2.3 PARTICIPANT REGISTRATION AND STATUS UPDATE PROCEDURES

Registration and status updates (e.g. when a participant is taken off protocol therapy and when a participant is taken off-study) will take place per CCR SOP ADCR-2, CCR Participant Registration & Status Updates found here.

2.3.1 Treatment Assignment Procedures

NOTE: The following for NCI CCR patient registration purposes only.

2.3.1.1 Cohorts

Number	Name	Description
1	RR CLL	Patients with relapsed/refractory CLL (Up to 24 patients)

2.3.1.2 Arms

Number	Name	Description
1	Dose Escalation	IL-15 by civ infusion at escalating doses of 0.5, 1, and 2 mcg/kg/day on days 1-5 of each 4-week cycle (max 6 cycles), with obinutuzumab by IV infusion at a dose of 100 mg on day 4, 900 mg on day 5, 1,000 mg on day 11, and 1,000 mg on day 18 of the first cycle; then 1,000 mg on day 4 of each subsequent cycle, to determine the MTD
2	Dose Expansion	An additional 3 to 6 patients to receive IL-15 by civ infusion at the MTD on days 1-5 of cycles 1-6 with obinutuzumab by IV infusion at a dose of 100 mg on day 4, 900 mg on day 5, 1,000 mg on day 11, and 1,000 mg on day 18 of the first cycle; then 1,000 mg on day 4 of each subsequent cycle (Total 9 patients at MTD)

2.3.1.3 Treatment Assignment

The study is single-arm, open-label and non-randomized; i.e., subjects in Cohort 1 are directly assigned to Arm 1 or Arm 2 based on the dose level/arm open to enrollment.

2.4 BASELINE EVALUATION

The following should be performed prior to the first dose of rhIL-15 unless otherwise noted; tests performed as part of screening do not need to be repeated if they were performed within the specified window prior to the first dose of rhIL-15.

2.4.1 Clinical Evaluations

- Required within 28 days:
 - Medical history (interim)
 - Physical examination, including weight, and vital signs (i.e., temperature, pulse, respiratory rate, and blood pressure); review of concomitant medications and symptoms/side effects; and, assessment of performance status

2.4.2 Laboratory Evaluations

NOTE: Results from outside NIH are accepted.

Version Date: 09/14/2021

- Required within 7 days:
 - o Urine and/or serum HCG in WOCBP
- Required within 14 days:
 - o CBC with differential
 - O Chemistry panels, including: Acute Care Panel (sodium, potassium, chloride, CO₂, glucose, BUN, creatinine), Mineral Panel (serum calcium, phosphate, magnesium and albumin), Hepatic Panel (alkaline phosphatase, ALT, AST, total and direct bilirubin), and 24-hour urine creatinine clearance (if needed measure CrCl if serum creatinine >1.5mg/dl)
 - o Others: LDH, Uric acid, Total protein
 - o Coagulation panel, including: PT/INR and aPTT
 - TSH with reflex T3 and free T4
 - Urinalysis (with microscopic examination if abnormal)
 - o HLA typing (A, B, C, DR, DQ)
 - Serum protein electrophoresis with immunofixation (SPEP)
 - o Serum free light chains, quantitative serum immunoglobulin (IG) levels
 - o C-reactive protein (CRP)
 - o Beta-2 microglobulin (B2M)
 - Haptoglobin, direct antiglobulin test (DAT)
 - o Iron panel (includes ferritin, transferrin, iron), folate, vitamin B12
 - o Viral studies (serologies CMV and EBV).
- Required within 28 days:
 - o Lymphocyte Phenotype: T, B and NK cell subsets
 - o Anti-Nuclear Antibody (ANA)
 - o Glucose-6-phosphate dehydrogenase (G6PD)
- Required within 3 months:
 - PB interphase FISH panel with probes for ATM (11q22.3), D12Z3 (12 cen),
 D13S319 (13q14.3), LAMP1 (13q34) and TP53 (17p13.1)
 - Karyotype
- Required, from any time point post-diagnosis (i.e., no time limit):
 - o IGVH mutation analysis

2.4.3 Imaging Studies

NOTE: Results from outside NIH are accepted. Other body areas may be imaged if clinically indicated.

- CT neck, chest, abdomen and pelvis (CT should be performed with IV and PO contrast, unless patient is allergic or has renal insufficiency; other imaging may be substituted at the discretion of the investigator [such as MRI])
- MRI of brain * (in patients with known or suspected involvement of CNS)

Version Date: 09/14/2021

*NOTE: The MRIs to be done in this study may involve the use of the contrast agent gadolinium, if clinically indicated. The risks associated with MRIs and contrast are discussed in the consent form and section 12.5.2

2.4.4 Other Procedures

- Flow cytometry will be performed on peripheral blood for both diagnostic and staging purposes (only NIH results accepted; NCI Laboratory of Pathology)
- Bone marrow aspiration and biopsy (within 3 months)

2.4.5 Research Correlates

NOTE: See Section 5 for additional information. The following sample types will be collected for correlative research studies:

[figure not shown]
- Required:
 - o Blood samples for lymphocyte subset testing and circulating tumor DNA
 - o Blood, buccal swab, or saliva for germline DNA
- Optional:
 - o Blood samples for ADCC of obinutuzumab, tissue immune cell subset comparison
 - o Bone marrow biopsy
 - o Tumor biopsy

Version Date: 09/14/2021

3 STUDY IMPLEMENTATION

3.1 STUDY DESIGN

To determine the MTD, and safety and toxicity profile of the combination of civ IL-15 and obinutuzumab, a non-randomized, open-label, single arm, single institution Phase I study will be conducted at the NCI. Each cycle of treatment is 28 days or 4 weeks, and a maximum of 6 cycles will be administered. Patients will be treated with civ IL-15 at dose levels of 0.5,1 or 2 mcg/kg/day on days 1-5 of cycles 1-6. Obinutuzumab (IV) will be administered at a dose of 100 mg on day 4, 900 mg on day 5, 1,000 mg on day 11, and 1,000 mg on day 18 of cycle 1; then 1,000 mg on day 4 of each subsequent cycle.

Study treatment will continue for as long as:

- Subject is deriving clinical benefit (complete remission [CR], partial remission [PR], or stable disease [SD]), and
- Subject is not experiencing any unacceptable toxicity (i.e., dose-limiting toxicity as found in Section 3.2 or toxicity requiring hold as defined in Section 3.5 lasting longer than two weeks)

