3.2 Dose-Limiting Toxicity

Dose-limiting toxicities are defined as: any grade 3, 4, or 5 toxicity if not incontrovertibly due to disease progression or an extraneous cause, and deemed possibly, probably or definitely related to IL-15 or obinutuzumab by the PI or designee during the first 28 days of treatment, with the following exceptions:

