3.2.1 Hematological Exceptions

- Grade 3 or 4 lymphocytopenia without clinical signs of infection grade 2 or above.
- Grade 3 or 4 neutropenia without clinical signs of infection grade 2 or above.
- Grade 3 or 4 thrombocytopenia lasting fewer than 5 days and not associated with bleeding or purpura.
- Grade 3 leukocytosis (WBC > 100,000/mm3) in the absence of signs of leukostasis or other toxicities possibly related to the expansion of activated cells.

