3.5.2.7 Thrombocytopenia

Severe and life-threatening thrombocytopenia has been reported during treatment with obinutuzumab in combination with chlorambucil or bendamustine. Fatal hemorrhagic events during Cycle 1 have also been reported in patients with CLL treated with obinutuzumab.

Monitor all patients frequently for thrombocytopenia and hemorrhagic events, especially during the first cycle. In patients with Grade 3 or 4 thrombocytopenia, monitor platelet counts more frequently until resolution and consider subsequent dose delays of obinutuzumab and chemotherapy or dose reductions of chemotherapy. Transfusion of blood products (i.e., platelet

Version Date: 09/14/2021

transfusion) may be necessary. Consider withholding concomitant medications which may increase bleeding risk (platelet inhibitors, anticoagulants), especially during the first cycle.

Each cycle may be delayed by up to two weeks until resolution of Grade 3 or 4 thrombocytopenia to Grade 1 or 2. If grade 3-4 thrombocytopenia occurs during Cycle 1, Day 4 and Day 5 doses of Obinutuzumab may still be administered, and Day 11 and Day 18 doses of Obinutuzumab delayed by up to a week until resolution of thrombocytopenia to Grade 1 or 2.

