3.10.1 Criteria for Removal from Protocol Therapy

- Completed planned treatment regimen/duration (i.e., up to 6 cycles)
- Confirmed hematologic or radiographic disease progression
- Unacceptable toxicity occurring at any time during treatment as listed in Section 3.2 or those toxicities listed in Section 3.5 that require treatment to be stopped.
- Intercurrent illness that prevents further administration of treatment
- Requirement for use of prohibited therapies as listed in Section 4.2
- Pregnancy
- Subject's requests to be withdrawn from protocol therapy
- Noncompliance with trial treatment or procedure requirements that requires removal in the opinion of the PI
- Investigator's decision to withdraw the subject
- Study is cancelled for any reason

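### Related Cycle 1 grade 3-4 thrombocytopenia lasting 5 days or more is a DLT that ends therapy under 3.1 and 3.10.1, but 3.5.2.7 permits delay and further dosing, and nothing says which prevails

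*Combined protocol and SAP*

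**What the plan says.** **DLT definition (3.2, 3.2.1).** A grade 3 to 5 toxicity is a DLT if it is not clearly due to progression or an extraneous cause and is "deemed possibly, probably or definitely related to IL-15 or obinutuzumab by the PI or designee during the first 28 days of treatment". One of the exceptions is "Grade 3 or 4 thrombocytopenia lasting fewer than 5 days and not associated with bleeding or purpura". A related event that reaches 5 days therefore falls outside the exception and is a DLT.

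**Continuation (3.1).** Treatment goes on only while this condition holds: "Subject is not experiencing any unacceptable toxicity (i.e., dose-limiting toxicity as found in Section 3.2 or toxicity requiring hold as defined in Section 3.5". Read to its end, the bracket covers "dose-limiting toxicity as found in Section 3.2 or toxicity requiring hold as defined in Section 3.5 lasting longer than two weeks".

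**Removal (3.10.1).** The grounds for stopping protocol therapy include "Unacceptable toxicity occurring at any time during treatment as listed in Section 3.2". This entry sets no minimum duration.

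**Thrombocytopenia management (3.5.2.7).** "Each cycle may be delayed by up to two weeks until resolution of Grade 3 or 4 thrombocytopenia to Grade 1 or 2". For grade 3-4 events in Cycle 1, "Day 4 and Day 5 doses of Obinutuzumab may still be administered", and the section then provides for "Day 11 and Day 18 doses of Obinutuzumab delayed by up to a week until resolution of thrombocytopenia to Grade 1 or 2". It does not separate events that are DLTs from those that are not, and does not refer to 3.2 or 3.10.1.

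**The concern.** Two sets of rules cover the same event. Under one, a related grade 3-4 platelet fall that reaches 5 days in the first 28 days ends protocol therapy. Under the other, the investigator may wait for recovery to Grade 1 or 2 and then give the next dose. Two patients with the same DLT could be handled in opposite ways, and each course could be defended or faulted by citing a different section.

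The event is a realistic one. Both agents' adverse event lists in Section 14 include decreased platelet count, Section 12.4 says the toxicities of the two drugs may overlap and names thrombocytopenia, and 3.5.2.7 singles out the first cycle for monitoring. Safety and toxicity profile are part of the primary objective, so it matters whether a patient with a DLT receives more study drug, and whether later-cycle toxicity and response data come from such patients.

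**Working it through.** **1. The plan's own figure that depends on DLTs.** Section 10.2 tabulates the probability of escalating at true DLT rate p. Under Table 5 this is

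P = (1-p)^3 + 3p(1-p)^2 × (1-p)^3.

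For p = 10, 20, 30, 40, 50 and 60% this gives 0.906, 0.709, 0.494, 0.309, 0.172 and 0.082, which matches the printed 0.91, 0.71, 0.49, 0.31, 0.17 and 0.08. The formula uses only the number of DLTs. What happens to a patient after a DLT does not enter it.

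**2. How far the delay and the DLT limit overlap.** Let t be the onset day and d the duration, with recovery to Grade 1 or 2 on day t + d. A dose scheduled on day s, with allowed delay L, uses the delay when s < t + d ≤ s + L. A related event is a DLT when d ≥ 5.

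| Dose | s | L | Onset days | Combinations using the delay | Of these, d ≥ 5 |
|---|---|---|---|---|---|
| Cycle 1 Day 11 | 11 | 7 | 1-11 | 11 × 7 = 77 | 7 × 7 + 6 + 5 + 4 + 3 = 67 |
| Cycle 1 Day 18 | 18 | 7 | 1-18 | 18 × 7 = 126 | 14 × 7 + 6 + 5 + 4 + 3 = 116 |
| Cycle 2 Day 1 (day 29) | 29 | 14 | 1-28 | 28 × 14 = 392 | 25 × 14 + 13 + 12 + 11 = 386 |

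These count possible day combinations. They are not patient probabilities, because the documents give no distribution of onset or duration.

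The Cycle 2 row needs care. For onset on days 25 to 28, the fifth calendar day (t + 4) is day 29 or later, so DLT status is unclear. With onset limited to days 1 to 24, all 24 × 14 = 336 combinations last at least 5 days, and the fifth day falls inside the window.

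**3. Single cases.**
- Onset Day 6, still present on Day 11: 11 - 6 = 5 days have passed. A related event is already a DLT on the day the dose is due, when 3.5.2.7 allows a delay.
- Onset Day 7, still present on Day 11: 4 days have passed, or five calendar days counting the onset day. The protocol does not say how days are counted, so the threshold on Day 11 itself is onset by Day 6 or Day 7. Either way, the earliest recovery on Day 12 gives d = 5.
- Onset Day 11: recovery on Days 12 to 15 (d = 1 to 4) fits both rules. Recovery on Days 16 to 18 (d = 5 to 7) does not.

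**4. Where there is no conflict.** Events judged unrelated are not DLTs. Related events under 5 days without bleeding or purpura are excepted. Both can follow 3.5.2.7 without contradicting 3.1 or 3.10.1.

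**The case against.** **The two-week wording in 3.1.** The phrase shows that 3.1 expects Section 3.5 holds and tolerates them for up to two weeks. That is correct, but on the natural reading it qualifies those holds and not DLTs. Even if it covered both, 3.10.1 has no such limit.

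**A harmonizing reading.** The end of 3.2.2 sends management of the listed exceptions to Section 3.5, and 3.5.2.7 is permissive. One could hold the dose while the event evolves and apply 3.1 and 3.10.1 once it becomes a DLT. This is the strongest point. It shows that the documents do not compel dosing: one section permits what another forbids. It does not settle the matter, because the exception ends at 5 days while the delays run to 7 and 14, and no section states the order of precedence. By contrast, the neutropenia exception in 3.2.1 has no time limit, so the two-week delay in 3.5.2.6 does not meet this problem.

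**Stronger readings that a reader might infer.**
- *That the delay lowers the DLT count and biases the MTD.* The documents do not support this. Section 3.3 uses the DLT definition in 3.2, and nothing in 3.5.2.7 removes DLT status. The replacement rules in 3.3 and 10.2 apply only to patients without a DLT. Under-reporting would be a failure of conduct at this single center, where the team meets weekly on each patient (7.4.1). It does not follow from the text.
- *That the full one-week and two-week delays can never be used consistently.* This is also too strong. Thrombocytopenia judged unrelated can use them in full, and such events are plausible because progressive marrow failure with low platelets is one of the criteria for active disease in 2.1.1.4.

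**Conclusion.** The contradiction stands for a defined group: grade 3-4 thrombocytopenia at least possibly related to rhIL-15 or obinutuzumab, in the first 28 days, lasting 5 days or more. For these patients 3.1 and 3.10.1 end protocol therapy and 3.5.2.7 permits it to continue. The group is not a corner case among related events that use the delay, since most of the allowed delay lies beyond the 5-day limit.

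The consequence is limited to patient disposition. Table 5 decisions, the escalation probabilities and the sample size do not change. What is left undefined is whether a patient with a DLT receives further study drug, and therefore that patient's safety and the later exposure, toxicity and response data. Section 10.2 plans 12 to 21 evaluable patients with 9 at the MTD, so one such patient would be 1/9 = 11% of the MTD group.

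This rests on reading the two-week phrase in 3.1 as applying to holds only (though 3.10.1 gives the same result without it) and on the day-counting convention shown above. How many patients would be affected cannot be estimated from the documents.

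**What to change.** Reconcile 3.1, 3.2.1, 3.5.2.7 and 3.10.1 so that a single rule states what happens to a patient whose related Cycle 1 grade 3-4 thrombocytopenia reaches 5 days. Whether that patient stops or continues is the sponsor's clinical choice, and this review takes no position on it. Add a cross-reference in 3.5.2.7 to 3.2 and 3.10.1, so that anyone using the delay provision sees how it relates to DLT status and removal.

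The cost is protocol wording only. No additional patients, tests or changes to the escalation design are needed.

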3.2 Dose-Limiting Toxicity

Dose-limiting toxicities are defined as: any grade 3, 4, or 5 toxicity if not incontrovertibly due to disease progression or an extraneous cause, and deemed possibly, probably or definitely related to IL-15 or obinutuzumab by the PI or designee during the first 28 days of treatment, with the following exceptions:

3.2.1 Hematological Exceptions

- Grade 3 or 4 lymphocytopenia without clinical signs of infection grade 2 or above.
- Grade 3 or 4 neutropenia without clinical signs of infection grade 2 or above.
- Grade 3 or 4 thrombocytopenia lasting fewer than 5 days and not associated with bleeding or purpura.
- Grade 3 leukocytosis (WBC > 100,000/mm3) in the absence of signs of leukostasis or other toxicities possibly related to the expansion of activated cells.

3.2.2 Non-Hematological Exceptions

- Transient (< 24 hours) grade 3 hypoalbuminemia, hypokalemia, hypomagnesemia, hyponatremia or hypophosphatemia which responds to medical intervention.
- Non-sustained (< 7 days) grade 3 liver function test (ATL, AST, alkaline phosphatase, total or direct bilirubin) abnormalities in the absence of clinical signs of hepatic dysfunction (lethargy, confusion, anorexia, pruritus, tremor); for patients with baseline grade 1 elevations, any increase ≥ 10 x baseline will be considered dose-limiting and these patients will be closely monitored for liver function abnormalities.
- First grade 3 infusion reaction associated with obinutuzumab administration (occurring

Version Date: 09/14/2021

within 24 hours of the dose). Infusion reactions will be managed as outlined in Section 3.5.

• Grade 3 tumor lysis syndrome (TLS) and non-sustained (<7 days) grade 3-4 metabolic abnormalities related to TLS. TLS will be managed as outlined in Section 3.5.

Management and dose modifications associated with the above adverse events are outlined in Section 3.5. Occurrence of any of the adverse events listed above after the first 28 days of treatment will lead to permanent discontinuation of protocol therapy, but will not be deemed a DLT for purposes of dose escalation.

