12.4 EVALUATION OF BENEFITS AND RISKS/DISCOMFORTS

For patients with relapsed/refractory CLL, complete response rates for the six drug and drug combinations approved are no greater than 30%. Obinutuzumab, a humanized type 2 anti-CD20, is approved in combination with chlorambucil for CLL, and is thought to directly activated ADCC. Agents that may enhance ADCC, such as rhIL15, could improve efficacy of obinutuzumab. Although the clinical benefit of these drug(s) has not yet been established, the intent of offering this treatment is to provide a possible therapeutic benefit, and thus the patient will be carefully monitored for tumor response and symptom relief in addition to safety and tolerability.

Version Date: 09/14/2021

Since fevers, rigors, lymphopenia, LFT elevations, and thrombocytopenia occurred during IL-15 infusion in the continuous IV trial, and since obinutuzumab will be given concomitantly, these toxicities may overlap. However, all IL-15-related reactions were transient and resolved by Day 8 of each cycle (third post-infusion day). Obinutuzumab manufacturer recommendations for IRR and TLS prophylaxis and criteria for discontinuing therapy in the event of either will be followed.

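### Read literally, the closing stop rule of Section 3.2.2 ends treatment after day 28 for the DLT exceptions that Section 3.5 manages; it should name DLT-type toxicity instead

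*Combined protocol and SAP*

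**What the plan says.** Section 3.2 defines a DLT in general terms: grade 3 to 5 toxicity, not clearly due to progression or an outside cause, and "deemed possibly, probably or definitely related to IL-15 or obinutuzumab by the PI or designee during the first 28 days of treatment". Sections 3.2.1 and 3.2.2 then list the exceptions, among them "Grade 3 or 4 neutropenia without clinical signs of infection grade 2 or above" and "Grade 3 or 4 thrombocytopenia lasting fewer than 5 days and not associated with bleeding or purpura". Others are uncomplicated lymphocytopenia, grade 3 leukocytosis without leukostasis, brief electrolyte changes, short-lived grade 3 liver test abnormalities, a first grade 3 infusion reaction to obinutuzumab, and grade 3 tumor lysis syndrome (TLS).

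Section 3.2.2 closes with two adjacent sentences. The first reads "Management and dose modifications associated with the above adverse events are outlined in Section 3.5". The second reads "Occurrence of any of the adverse events listed above after the first 28 days of treatment will lead to permanent discontinuation of protocol therapy", and adds that such an occurrence "will not be deemed a DLT for purposes of dose escalation".

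Section 3.5 then gives management rules for most of these event types. Section 3.1 (continuation of treatment) and Section 3.10.1 (removal from therapy) both tie unacceptable toxicity to Section 3.2.

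**The concern.** The two closing sentences appear to speak of the same events, yet one sends them to Section 3.5 to be managed and the other makes them a permanent stop once day 28 has passed. A clinician who follows the stop as written takes patients off treatment for events that the DLT definition deliberately excuses and that Section 3.5 manages. A clinician who follows Section 3.5 departs from a mandatory stopping rule.

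Such event types are foreseeable in later cycles. Section 12.4 records that "lymphopenia, LFT elevations, and thrombocytopenia occurred during IL-15 infusion in the continuous IV trial", and describes these reactions as transient in each cycle. It gives no grades, so it does not show how often they would reach grade 3 or 4. At stake are how long patients stay on treatment in cycles 2-6 and, through that, the descriptive adverse event frequencies and the response results.

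**Working it through.** No planned figure is in dispute, so the check sets the texts side by side.

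**Step 1: what stands above the sentence.** The general DLT definition (3.2) is there, but it itemises no events. The bullets in 3.2.1 and 3.2.2 are exceptions. One bullet also carries a dose-limiting event: for patients with grade 1 liver test elevations at baseline, a rise to at least 10 times baseline. Apart from that clause, the itemised events are all exceptions.

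**Step 2: literal stop against Section 3.5, for onset after day 28.**

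| Event itemised in 3.2.1-3.2.2 | Closing sentence, read literally | Section 3.5 |
|---|---|---|
| Grade 3-4 neutropenia without grade 2+ infection | Permanent stop | Cycle may wait up to two weeks (3.5.2.6) |
| Grade 3-4 thrombocytopenia under 5 days, no bleeding or purpura | Permanent stop | Cycle may wait up to two weeks (3.5.2.7) |
| Lymphocytopenia, electrolyte or short liver test abnormalities | Permanent stop | Infusion may go on while laboratory abnormalities listed in 3.2 are corrected (3.5.1) |
| First grade 3 infusion reaction | Permanent stop | Restart rhIL-15 once symptoms resolve and consider restarting obinutuzumab; permanent stop if grade 3 symptoms recur at rechallenge (3.5.2.3) |
| Grade 3 TLS | Permanent stop | Supportive care; prophylaxis before later infusions as needed (3.5.2.4) |

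Most of the right-hand column is permissive. The restart of rhIL-15 is an instruction, so that row is a direct clash. Section 3.4.2 fits the same picture: it prescribes premedication for an infusion that follows a grade 3 reaction.

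**Step 3: is the literal rule plausible?** It makes a 4-day thrombocytopenia without bleeding a stop. A 10-day episode, or one with bleeding, is not an itemised event, so the sentence itself does not reach it. The milder event is treated more severely than the worse one. It also removes most of the use of the delay provisions in cycles 3-6, because any new event that would delay those cycles arises after day 28.

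**Step 4: what was meant?** Saying that a late event "will not be deemed a DLT for purposes of dose escalation" has a purpose only for events that would otherwise be DLTs; the exceptions never are. Section 3.1 makes a DLT under 3.2 a reason to end treatment. Section 3.10.1 does the same for unacceptable toxicity at any time, by reference to 3.2. All three point to DLT-type toxicity that arises late.

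**Step 5: the intended reading against Section 3.5.** Some DLT-type events also meet the delay text: related grade 3-4 thrombocytopenia of 5 days or more, or with bleeding or purpura (3.5.2.7), and related grade 3-4 neutropenia with grade 2 or higher infection (3.5.2.6). Here 3.2.2 and 3.10.1 are mandatory, while the delay text only permits. The stop most naturally prevails, but no sentence says so.

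**Step 6: what does not change.** Section 10.2 bases the MTD on DLTs in the first cycle. Its escalation table follows from P = (1-p)^3 + 3p(1-p)^2 x (1-p)^3, where p is the first-cycle DLT rate. For p = 10% to 60% this gives 0.906, 0.709, 0.494, 0.309, 0.172 and 0.082, against the stated 0.91, 0.71, 0.49, 0.31, 0.17 and 0.08. All six agree, and events after day 28 do not enter the formula.

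**The case against.** The best defence is that the wording is ambiguous and the meaning can be recovered. The general DLT definition also stands above the sentence, the liver clause is itself dose-limiting, Section 3.3 says that DLT is defined above, and Section 3.10.1 speaks of unacceptable toxicity as listed in 3.2. A reader could therefore take the events listed above to be DLTs. That is very likely what was meant, and it rules out saying that nothing but exceptions is listed. It does not repair the sentence. The preceding sentence uses almost the same phrase for the events sent to Section 3.5, and a mandatory stop should not have to be corrected by inference.

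A reader might also infer that, even on the intended reading, the protocol is deadlocked over thrombocytopenia of 5 days or more. The documents do not support that: a provision that a cycle may wait does not override a mandatory stop. Section 3.5.2.7 also keeps its own uses, for short episodes without bleeding, unrelated events and excepted cycle 1 events that delay cycle 2. Only a statement of precedence is missing.

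Nor does Section 3.5 lack any limit for infection. Section 3.5.2.5 bars obinutuzumab during active infection and, for patients who need antibiotics, says only that those without neutropenia may continue. That is not an explicit permanent stop, but it is a safeguard.

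Finally, this is a single-institution trial whose team discusses each patient at least weekly (7.4.1), which makes divergent practice less likely. That lowers the practical risk but leaves the text wrong.

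**Conclusion.** The point holds as a wording error in a mandatory stopping rule. Followed literally, the closing sentence of 3.2.2 ends treatment for events that the protocol elsewhere excuses and manages. The intent, to stop DLT-type toxicity arising after day 28, is clear from the rest of the sentence and from Sections 3.1 and 3.10.1.

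The effect is on exposure, adverse event frequency and response in cycles 2-6. The number of patients affected cannot be estimated, because the documents give no rates of these events by grade in later cycles. A reader might infer that dose finding is compromised; it is not, since late events count neither towards DLTs nor towards the MTD, and the sample size does not depend on them. The conclusion rests on the wording alone and needs no assumption about event rates.

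**What to change.** Replace the closing sentence of 3.2.2 with:

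> *Toxicities that would meet the DLT definition in 3.2, apart from timing, but occur after the first 28 days lead to permanent discontinuation of protocol therapy and are not counted as DLTs for dose escalation; events covered by the exceptions in 3.2.1-3.2.2 are managed under Section 3.5 whenever they occur.*

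Add one line to each of 3.5.2.6 and 3.5.2.7:

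> *The delay provisions apply only to events that are not stops under 3.2.2.*

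This keeps as stops related grade 3-4 thrombocytopenia of 5 days or more or with bleeding or purpura, and related grade 3-4 neutropenia with grade 2 or higher infection. If the sponsor prefers to allow a delay for thrombocytopenia of 5 days or more without bleeding or purpura, 3.5.2.7 should say so and the new sentence in 3.2.2 should carry that exception.

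The cost is one small amendment, with IRB approval before it takes effect. It adds no patients, visits or procedures.
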